Official Title: Effect of Preoperative Dexpantenol Moisturizer on the Prevention of Angular Cheilitis After Pediatric Adenotonsillectomy: A Randomized Controlled Trial

NCT Number: NCT07002632

Document Date: July 7, 2021

MATERIALS AND METHODS

This prospective, randomized, controlled study was designed and conducted in strict adherence to the ethical principles of the Declaration of Helsinki. The study protocol was approved by the institutional ethics committee (approval date: 07.07.2021; number: 309) and written informed consent was obtained from patients' parents. This study was designed and reported in compliance with the CONSORT (Consolidated Standards of Reporting Trials) guidelines for randomized controlled trials. A CONSORT flow diagram illustrating the progress of participants through the trial phases is included (**Figure 1**). Given the limited prior literature, confined to a single pilot study by England et al. [4], a precise power analysis was not feasible. Initially, the target sample size was set at 60 patients over a 3-year period. To enhance statistical power, enrollment continued throughout the planned period, ultimately yielding a sample of 106 participants.

A total of 106 children aged 3-15 years scheduled for adenotonsillectomy between July 2021 and July 2024 at a tertiary referral ENT facility were enrolled in the study. Patients were randomized into study and control groups using computer-generated random numbers. In the study group, a water-in-oil emulsion formula containing 5% dexamethasone (Bepanthol® Derma moisturizing cream, Bayer Türk Kimya San. Ltd. Şti. İstanbul, Türkiye) was administered to both oral commissures as a moisturizer immediately before mouth gag insertion while the control group received no cream. The Brodsky Grading Scale was used to assess pre-operative tonsillar hypertrophy. Pre-operative Mallampati scores of patients were also recorded. The conventional cold steel tonsillectomy technique was preferred in all patients to ensure consistency. Under the supervision of the same senior surgeon, all surgeries were performed by the same resident. Under general anesthesia, the Boyle Davis mouth gag was inserted. The size of the tongue depressor of the Boyle Davis mouth gag was recorded. Prior to incision, the distance between the upper and lower central incisors was measured using a ruler.

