Adenoideectomy was performed first using a standard curette technique under direct visualization with a mirror. Following excision of adenoid tissue, gauze packs were placed in the nasopharynx to achieve hemostasis and bipolar cautery was applied when necessary. Subsequently, tonsillectomy was performed using the cold steel dissection technique. Once the pericapsular plane was identified, the tonsils were dissected bluntly and excised. Bipolar electrocoagulation and nonabsorbable 2.0 silk ties were utilized simultaneously to manage hemorrhage in all surgeries. The inferior tonsil poles were consistently ligated with 2.0 silk ties. The surgical time was recorded. A single dose of prophylactic cefazolin sodium (25 mg/kg) was administered parenterally to all patients preoperatively, and in the postoperative period, all patients received oral paracetamol suspension (20 mg/kg) three times daily for pain control.

Postoperative evaluations were conducted by a senior surgeon who was unaware of the patients' group assignments. On the first postoperative day, patients were assessed for the presence of AC and the severity of pain. The presence of AC was assessed and recorded as either present or absent. Pain intensity was evaluated by the patients' parents by utilizing the Wong-Baker Faces Pain Rating Scale, which ranges from 0 to 10 points. All patients underwent reevaluation for the same measures on the seventh day postoperatively.

Statistical Analysis

Statistical analyses were conducted using the Statistical Package for the Social Sciences (SPSS) version 26.0 (IBM Corp., Armonk, NY, USA; RRID:SCR_002865). Categorical variables were presented as frequencies and percentages (%). Numerical variables were expressed as mean and standard deviation (SD). The comparison of categorical variables was performed using the Pearson Chi-Square test. The normality of numerical variables was assessed using the Kolmogorov-Smirnov test, and variables following a normal distribution

were compared using the Independent Samples T-Test. Binary logistic regression analysis was used to evaluate the independent effect of topical dexamethasone use on the occurrence of AC on postoperative first day and first week. Odds ratios (ORs) with 95% confidence intervals (CIs) were calculated. The model's explanatory power was assessed using Nagelkerke R². A p-value less than 0.05 was considered statistically significant.

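### The logistic regression of angular cheilitis has no provision for an arm with no or very few events; if cream-arm rates are about 5% or less, its OR, CI and p-value may be unusable or conflict with the chi-square

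*Combined protocol and SAP*

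**What the plan says.** The outcome is binary: "The presence of AC was assessed and recorded as either present or absent". It is recorded on the first postoperative day and again on the seventh.

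The Statistical Analysis section applies two methods to it. For the crude comparison, "The comparison of categorical variables was performed using the Pearson Chi-Square test". For the effect estimate, "Binary logistic regression analysis was used to evaluate the independent effect" of the topical product on AC at each of the two time points, and "Odds ratios (ORs) with 95% confidence intervals (CIs) were calculated". The threshold is common to all tests: "A p-value less than 0.05 was considered statistically significant".

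The section does not name the estimator, the type of confidence interval, the covariates, any procedure for zero or sparse cells, or which of the two analyses decides if they disagree.

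Materials and Methods describes enrolment as "ultimately yielding a sample of 106 participants" and says that "a precise power analysis was not feasible". It gives no AC rate, event count or arm size.

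**The concern.** The OR is the only effect measure that the plan names for AC. Ordinary logistic regression estimates it well when both arms have a reasonable number of events. It breaks down when one arm has none, and its Wald test loses power when one arm has one or two.

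The trial tests a preventive measure, so a low count in the cream arm is what success would look like. The report could then show a significant chi-square beside an OR near zero, a CI running from zero to infinity and a p-value near 1, all from the same table. The plan does not tell a reader which to believe.

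**Working it through.** **Inputs.** From the documents: 106 children, binary outcome, threshold 0.05. Assumed because the documents do not say: 53 per arm, two-sided tests, no missing visits, no covariates, maximum-likelihood fit with Wald inference, and the true AC rates shown below. The plan has no power figure to reproduce. Counts are written cream v control.

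**Step 1: zero events in the cream arm, 0 v 6 of 53.**
- Pearson: χ² = 106 × (0×47 − 53×6)² / (53 × 53 × 6 × 100) = 6.36, p = 0.012. Fisher exact p = 0.027.
- Maximum likelihood: OR = (0×47)/(53×6) = 0, so log OR is −∞ and no finite estimate exists. A fit stopped at 20 iterations gave a coefficient of −19.1, a standard error of about 5,500 and Wald p = 0.997. The OR and standard error depend only on where the iteration stops.
- Firth: in an unadjusted 2×2 table this equals adding ½ to each cell. OR = (0.5 × 47.5)/(6.5 × 53.5) = 0.068, profile penalised-likelihood 95% CI 0.0005 to 0.603, p = 0.011.
- Risk difference: 0 − 6/53 = −11.3 percentage points. Wilson limits are 0 to 0.0676 (cream) and 0.0529 to 0.2258 (control). The Newcombe lower limit is −0.1132 − (0.2258 − 0.1132) = −0.2258; the upper limit is −0.1132 + √(0.0676² + (0.1132 − 0.0529)²) = −0.0226. The CI is −22.6 to −2.3 points, finite despite the empty cell.

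**Step 2: one event in the cream arm, 1 v 7 of 53.**
- Pearson: χ² = 106 × (1×46 − 52×7)² / (53 × 53 × 8 × 98) = 4.87, p = 0.027.
- Wald: log OR = ln(46/364) = −2.069; SE = √(1 + 1/52 + 1/7 + 1/46) = 1.088; z = −1.90, p = 0.057.
- Firth p = 0.030; Fisher p = 0.060.

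**Step 3: how often an arm is empty.** P(no events in 53) = (1 − rate)^53: 59% at a true rate of 1%, 34% at 2%, 20% at 3%, 7% at 5%, 0.4% at 10%.

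**Step 4: how often the two analyses conflict.** Exact binomial enumeration of all tables at 53 per arm, with a zero cell counted as Wald non-significant:

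| True rates, cream v control | Power: Wald | Power: Pearson | Power: Firth | Pearson significant, Wald not | Fisher significant, Wald not |
|---|---|---|---|---|---|
| 2% v 10% | 8% | 41% | 33% | 33.1% | 15.0% |
| 2% v 15% | 30% | 72% | 67% | 41.7% | 28.3% |
| 5% v 20% | 57% | 67.5% | 65% | 10.5% | 6.4% |
| 10% v 20% | 28% | 30% | 29% | 2.2% | 0.4% |

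**Step 5: does keeping Pearson beside Firth remove the conflict?** Not fully. A table of 0 v 4 gives Pearson p = 0.041 and Firth p = 0.050. Pearson is significant and Firth is not in 7% of trials at 2% v 10%. One of the two has to be named as deciding.

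**Step 6: unequal arms.** Against zero cream-arm events, Pearson first reaches p < 0.05 at 4 control events with 53:53. For cream:control splits from 63:43 to 43:63 the threshold lies between 3 and 6.

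**The case against.** The strongest reply is that the trigger is not in the documents. A reader might infer from the sample size alone that the model will fail, or that failure is likely across most plausible rates. Neither follows. What matters is the number of events in the smaller cell, not the total of 106, and no rate is given for either visit. At a cream-arm rate of 10% the conflict is rare (about 2%), and nothing shows that day 1 is sparse.

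Part of the conflict also comes from the chi-square. At 0 v 4 the expected event count is 2 per arm and Fisher gives p = 0.118, so Pearson's significance is itself doubtful. At 2% v 10% only 15 of the 33 percentage points remain if Fisher replaces Pearson. With a zero cell and equal arms, the conflict is firm only from 0 v 6.

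Maximum likelihood and Wald are the usual reading of the plan, not its words. A likelihood-ratio test would give p = 0.003 at 0 v 6, though the OR would still not be finite. A reader might also take the reference to an independent effect as showing that many covariates will bias the OR. The plan lists none, so no size can be put on that.

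Finally, the harm is partly contained. Frequencies and percentages are to be reported, so an empty cell would be visible, and the Wald error shown here is towards missing an effect.

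All of this stands. It limits the point to a conditional one, but supplies neither the missing rule for sparse cells nor the missing statement of which analysis decides.

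**Conclusion.** The point holds in conditional form. Followed as written and read in the ordinary way, the plan gives no usable OR or CI at any visit where the cream arm has no AC, and a conservative Wald test where it has one or two events. The chance that Pearson is significant and Wald is not depends on rates that the documents do not give. Under the assumptions listed it is between about 10% and 42% in the three scenarios with a cream-arm rate of 2% or 5%, and about 2% at 10% v 20%. The matter is therefore important only if the cream-arm rate is about 5% or less. The documents do not show that this is so, nor that the analysis has failed.

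**What to change.** 1. Report AC counts by arm at day 1 and at one week.
2. Take the OR, 95% CI and p-value from Firth penalised logistic regression with profile penalised likelihood, at least at any visit with a zero or sparse cell, and state that Wald results are not used there.
3. Report the risk difference with a Newcombe 95% CI alongside.
4. State that the Firth result decides the treatment comparison and that the chi-square is descriptive. Without this sentence two disagreeing p-values remain possible.

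The text is in the past tense with enrolment complete, so this can be done on the existing data. The cost is a few sentences of wording, possibly a different software routine, and slight shrinkage of the OR towards no effect when events are common. Power is little affected in that case: at 10% v 30% it is 75% for Firth and 73% for Wald.
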